## 11. Statistical considerations

Our null hypothesis is that 20% of patients will require hospitalization by day 28. This is based on internal data (from [name] EPIC analysis team at Johns Hopkins Hospital) that demonstrates an overall hospitalization rate of 14% and a hospitalization rate of 18-20% in patients 60 years old and older. We expect that each of the investigational treatment will reduce it to 2% or lower.

The sample size of 20 in each investigational arm is determined based on the comparison to the control arm. The design gives us 80% power to detect a decrease in hospitalization rate from 20% in the control arm to 2% in the treatment arm, based on a one-sided Fisher's exact test with type I error of 0.25.

If we observe 1 or less patient hospitalized within 28 days since randomization in an investigational arm, we reject the null rate of 20% in favor of 4% or less hospitalization rate with that treatment. **Table 1** lists the 90% confidence intervals for various scenarios of observed proportion of hospitalized patients. **Table 2** shows the probability of observing 1 or less hospitalized patient under various true rates. If the true rate is 20% in Arm B or Arm C, the chance of observing only 1 or less hospitalization is low at 7%; and that chance is greater than 80% if the true hospitalization rate is 4% or lower. Given this is a small study, and the true effect size is unknown, the estimates and safety generated in this trial will be used to inform power calculations of a larger, confirmatory trial.

**Table 1.** Confidence intervals for various observed proportions of hospitalized patients in each arm.

Observed # of hospitalizations (out of 20)	Observed hospitalization rate	90% CI (Wilson method)
0	0%	[0, 11.9%]
1	5%	[1.1%, 19.6%]
2	10%	[3.4%, 26.2%]
3	15%	[6.2%, 32.2%]
4	20%	[9.3%, 37.8%]
5	25%	[12.7%, 43.2%]
6	30%	[16.4%, 48.4%]
7	35%	[20.2%, 53.3%]
8	40%	[24.2%, 58.1%]

**Table 2.** True hospitalization rate and probability of observing 1 or less hospitalization for each arm.

True hospitalization rate	Probability of observing 1 or less hospitalization (out of 20 patients)
1%	98%
2%	94%
3%	88%
4%	81%
5%	74%
6%	66%
10%	39%
15%	18%
20%	7%
25%	2%

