## 3. Patient Selection

A total of 40 patients will be recruited.

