### 11.1. Analysis of primary endpoint:

The % of patients admitted to the hospital or died will be estimated for each arm as the proportion of patients who are hospitalized or die by day 28 since randomization along with 95% confidence interval. The secondary analysis of comparison between arms will be conducted using Fisher's exact test.

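### With 20 per arm, the one-sided Fisher test at 0.25 has an actual type I error of only about 16%; Boschloo's exact test would raise power from 80% to 87% with the same 40 patients (optional efficiency gain)

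*Combined protocol and SAP*

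**What the plan says.** Section 11 of the combined protocol and SAP ties the sample size to the randomized comparison: "The sample size of 20 in each investigational arm is determined based on the comparison to the control arm". It states: "The design gives us 80% power to detect a decrease in hospitalization rate" "from 20% in the control arm to 2% in the treatment arm", using a one-sided Fisher's "exact test with type I error of 0.25". Section 3 gives the total: "A total of 40 patients will be recruited". Section 6.2 allocates them 1:1.

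Section 11 also has a separate single-arm rule. If at most 1 of 20 patients in an investigational arm is hospitalized within 28 days, the 20% null is rejected in favour of a rate of 4% or lower.

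Section 11.1 makes the primary analysis an estimate for each arm with a 95% confidence interval. It then says: "The secondary analysis of comparison between arms will be conducted using" Fisher's exact test. It gives no side or significance level for that comparison. The documents do not report the actual size of the Fisher test and mention no unconditional test.

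**The concern.** A one-sided level of 0.25 is a deliberate choice to tolerate false positives so that a small trial is less likely to miss a signal. Fisher's test conditions on the total number of admissions. When few events are expected, its attainable p-values are widely spaced and its actual error falls well below the nominal level. The error left unspent is power forgone.

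This matters because the randomized comparison is what the trial was sized on. It is also the only comparison that does not rely on a fixed 20% rate taken from hospital records. Section 4.1 allows standard-of-care drugs and vaccination in both arms, so the control rate may differ from that figure.

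**Working it through.** **Inputs.** 20 per arm, one-sided Fisher, level 0.25, control 20%, treated 2% (all section 11). The 4% alternative comes from the single-arm rule in section 11. T and C are the treated and control admission counts, taken as independent binomials with n = 20.

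**Step 1: rejection region of the Fisher test.** p(t, c) = Pr(T ≤ t | T + C = t + c), hypergeometric.
- 0 v 2: 190/780 = 0.244, reject.
- 1 v 3: (4,845 + 20 × 1,140)/91,390 = 27,645/91,390 = 0.302, do not reject.
- 1 v 4: (15,504 + 20 × 4,845)/658,008 = 0.171, reject.
- 2 v 4: 0.331, and 3 v 5: 0.347, do not reject.

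So for 0, 1, 2 or 3 treated admissions, rejection needs at least 2, 4, 5 or 6 in control.

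**Step 2: reproduce the plan's power.** Power = Σ Pr(T = t) × Pr(C ≥ c_t).

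| t | Pr(T = t), 2% | control needed | Pr(C ≥ c_t), 20% | product |
|---|---|---|---|---|
| 0 | 0.6676 | 2 | 0.9308 | 0.6214 |
| 1 | 0.2725 | 4 | 0.5886 | 0.1604 |
| 2 | 0.0528 | 5 | 0.3704 | 0.0196 |
| 3 | 0.0065 | 6 | 0.1958 | 0.0013 |

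The sum is 0.8027, so the stated 80% is right. Other readings do not give 80%: two-sided Fisher at 0.25 gives 64.1%, and one-sided Fisher at 0.025 gives 27.1%.

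**Step 3: actual type I error of the Fisher test.** Use the same region with one common rate in both arms. The error is 0.157 at 20% and 0.151 at 18%, with a maximum of 0.162 near 24%. As shares of the allowance, 0.157/0.25 = 63% and 0.162/0.25 = 65%.

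**Step 4: Boschloo's test.** It ranks outcomes by the Fisher p-value and chooses the cut-off so that the error, maximised over the common rate, stays within 0.25. The cut-off here is p ≤ 0.347, with maximum size 0.243 (near a common rate of 17%). The next attainable cut-off, 0.358, would give 0.263, which is too large.

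At low counts this adds three outcomes (treated v control). Their contributions to power at 20% v 2% are:
- 1 v 3: 0.2725 × 0.2054 = 0.0560
- 2 v 4: 0.0528 × 0.2182 = 0.0115
- 3 v 5: 0.0065 × 0.1746 = 0.0011

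The total is 0.0686, and 0.8027 + 0.0686 = 0.8713. Outcomes added at higher counts contribute almost nothing at these rates. No outcome that Fisher rejects is lost.

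**Step 5: comparison.**

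| | Fisher | Boschloo |
|---|---|---|
| Power, 20% v 2% | 80.3% | 87.1% |
| Power, 18% v 2% | 75.1% | 82.5% |
| Power, 20% v 4% | 69.0% | 80.4% |
| Type I error at 20% | 15.7% | 23.9% |
| Maximum type I error | 16.2% | 24.3% |

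The 18% row uses the lower end of the rate that section 11 gives for patients aged 60 and over. Fisher's test would need about 25 per arm to reach 87.1%, that is 2 × 25 − 40 = 10 more patients.

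**The case against.** The case for leaving Fisher's test in place is substantial.

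- **Nothing is misstated.** The 80% is correct and the type I error is controlled. Fisher's test is a defensible standard, and choosing between conditional and unconditional exact tests is partly preference. This stands.
- **The comparison is secondary.** Section 11.1 attaches no level, side or decision to it, and section 11 says the trial's estimates and safety data will inform a larger study. Those do not depend on the test. This lowers the priority, but section 11 still sizes the trial on this comparison at 0.25.
- **Most of the gain lies in one table.** The result 1 v 3 carries 5.6 of the 6.9 points, about four-fifths. A reader might infer that the trial would be called negative at 1 v 3. The documents do not support that, because 1 of 20 already meets the single-arm rule. What changes is that the randomized comparison would agree with it.
- **The power is bought with error.** At a 20% rate, false positives rise from 15.7% to 23.9%, about half as many again. A sponsor may prefer the lower figure when the nominal level is already lenient. That is a legitimate choice and best made explicitly.
- **The gain depends on the test.** Unconditional tests ordered by a pooled or unpooled Z statistic gain 5.6 points (85.9%), with maximum error 17.7%.

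**Conclusion.** The point holds as an optional efficiency gain. With 20 per arm, the planned test realises about 16% type I error against the 25% allowed. Boschloo's test gains about 7 points of power at 20% v 2% and about 11 at 20% v 4%, within the stated limit and with the same 40 patients.

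Two stronger readings are tempting, and neither is supported. One is that the trial is underpowered for its stated target or that its power is miscalculated; enumeration reproduces the 80%. The other is that Fisher's test spends only 16% of the permitted error. The 16% is the error itself, and the share spent is 63 to 65%.

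The figures assume exactly 20 evaluable patients per arm, independent binomial counts, no use of the randomization strata in the test, and the plan's hospitalization rates applied to the composite of hospitalization or death.

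**What to change.** Before outcome data are seen, in sections 11 and 11.1:

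1. Replace Fisher's exact test with Boschloo's unconditional exact test, one-sided at 0.25, for the between-arm comparison of hospitalization or death by day 28. This also supplies the side and level that section 11.1 lacks.
2. Restate the power as 87% for 20% v 2% and 80% for 20% v 4%, and report the maximum size of 24.3%.
3. State that the realised type I error at a 20% rate rises from 15.7% to 23.9%.

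The cost is wording only. The test is in standard software, and neither the sample size nor the data collection changes. A mid-P version is not an equivalent substitute because it does not guarantee size: unstratified, its error is 26.3% at a 20% rate, above the stated 0.25. If the sponsor prefers the lower realised error, keeping Fisher's test is acceptable, and a sentence giving its actual size of about 16% would make that choice visible.

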### 2.4. Primary endpoint

Percentage of people who are hospitalized or die by day 28.

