## 10. Study Calendar

	Day of study										
	Baseline/ screening	Treatment							Follow up ( $\pm$ 3 days)		
		-3 to 0	1	2	3	4	5	6	7 &	21	60
Eligibility	X										
Consent	X										
Randomization and drug dispensing*	X										
COVID-19 symptoms	X ^				X				X	X	X
Follow-up visit (can be in person, via telephone or via telemedicine)**				X					X	X	X
Review of medical record for hospitalization, death, etc a								X			
Both arms standard of care		X	X	X	X	X	X	X			
Experimental arm: Bicalutamide + camostat Treatment		X	X	X	X	X	X	X			
Adverse events, con meds (including OTC medications), new infections***			X						X	X	X
COVID-19 nasopharyngeal swab ^^	X								X	X	
Clinical and study blood collection (CMP b , CBC and differential, coagulation, d-dimer, CK, CRP, ESR, ferritin) ^^		X							X	X	
Ultrasensitive PSA + sex hormones c^^	X								X	X	
COVID-19 RNA testing (quantitative and qualitative) from blood, oral samples for research) ^^	X								X	X	
Additional research blood draw (1 tube) ^^	X								X	X	
SARS-CoV-2 antibody analysis ^^	X								X	X	

\*Study drug may be shipped to the patient. See section 4.6 for information relevant to drug dispensing.

Review of remaining pills and Study Drug Patient Diary may be conducted during a telemedicine visit.

Copies of the Study Drug Patient Diary may be submitted to study staff by phone, email, fax, or mychart

\*\*If patients are admitted, we will get information from the medical record.

\*\*\*Any new infection that occurs on study will be recorded. The site of infection and the source of culture (ie BAL, tracheal aspirate, sputum, blood, urine, etc.) will be recorded as well.

aThe following will be recorded daily (as available) from hospital records: symptoms (see Appendix A), temperature, heart rate, respiratory rate, systolic blood pressure, diastolic blood pressure, oxygen saturation, height, weight, oxygen requirements and supplementary oxygen use, procedures (including intubation, renal replacement therapy, vasopressor/inotropic support, ECMO, etc), intermediate care unit duration, intensive care unit duration

bCMP: Na, K, Cl, BUN, Cr, Ca, Tot Protein, Alb, bilirubin, AST, ALT, Alk phos, CO2

cSex hormones: estradiol, free testosterone, total testosterone, FSH, LH

& Day 7 labs may be collected +/- 3 days

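### The rule of at most 1 event in 20 does not establish a rate of 4% or less, and it counts hospitalizations only although the primary endpoint is hospitalization or death by day 28

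*Combined protocol and SAP*

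**What the plan says.** Section 11 (Statistical considerations) sets the null: "Our null hypothesis is that 20% of patients will require hospitalization by day 28". It supports the 20% with internal data showing "a hospitalization rate of 18-20% in patients 60 years old and older". The decision rule starts "If we observe 1 or less patient hospitalized within 28 days since randomization in an investigational arm" and ends "we reject the null rate of 20% in favor of 4% or less hospitalization rate with that treatment". The same paragraph describes the rule's behaviour at that lower rate: "that chance is greater than 80% if the true hospitalization rate is 4% or lower". Table 1 gives 90% Wilson intervals for observed counts out of 20. Table 2 gives the probability of seeing 0 or 1 hospitalization over a range of true rates.

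The primary endpoint in Section 2.4 is different: "Percentage of people who are hospitalized or die by day 28". Section 11.1 follows Section 2.4 and estimates, for each arm, the "proportion of patients who are hospitalized or die by day 28 since randomization along with 95% confidence interval". Death is collected: Section 6.12 records vital status and date of death for 60 days, and the Section 10 calendar includes "Review of medical record for hospitalization, death, etc". The primary objective (Section 2.1), the study design (Section 4.1) and the section on assessing the primary outcome (Section 6.7) speak of hospitalization only.

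**The concern.** There are two separate problems.

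First, the rule attaches to a pass a conclusion that the data cannot establish. Only 0/20 and 1/20 pass, and with either result the interval printed in the same section runs well above 4%. The 4% is a property of the design (a true rate at which the rule is likely to pass), but the sentence presents it as what is concluded once the data are in.

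Second, the rule does not count the primary endpoint. A patient who dies by day 28 without being admitted is a primary-endpoint event under Sections 2.4 and 11.1 but not an event under the rule. With a cut-off of one event in 20, where one patient has already been admitted, a single such death decides whether the arm passes.

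At stake are what a positive result is taken to mean, and whether the pass/fail decision agrees with the Section 11.1 estimate. Section 11 also says that the trial's estimates will inform the power calculation of a larger trial.

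**Working it through.** **Inputs.** From Section 11: n = 20 per arm, pass if X ≤ 1, null 20%, source range 18-20%, stated pass probabilities 7% at 20% and 81% at 4%, and 90% Wilson intervals of 0 to 11.9% (0/20) and 1.1% to 19.6% (1/20). From Sections 2.4 and 11.1: the composite endpoint.

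**1. Reproduce Table 2.** With X binomial (20, p), P(X ≤ 1) = (1−p)^20 + 20p(1−p)^19 = (1−p)^19 (1 + 19p).
- p = 0.20: 0.8^19 × 4.80 = 0.01441 × 4.80 = 0.0692. Stated: 7%.
- p = 0.04: 0.96^19 × 1.76 = 0.4604 × 1.76 = 0.810. Stated: 81%.
- p = 0.05: 0.736. p = 0.06: 0.660. p = 0.10: 0.392. p = 0.15: 0.176. Stated: 74%, 66%, 39%, 18%.

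Every row of Table 2 reproduces.

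**2. Reproduce Table 1 for the two passing results.** Wilson 90%, z = 1.645, z² = 2.706.
- 0/20: upper limit = z²/(n + z²) = 2.706/22.706 = 11.9%.
- 1/20: (0.05 + 0.0676 ± 1.645 × √(0.0475/20 + 2.706/1600))/(1 + 2.706/20) = (0.1176 ± 0.1049)/1.1353, giving 1.1% and 19.6%.

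These agree with the printed limits. The separate power statement also reproduces: full enumeration of the one-sided Fisher test at 0.25, 20 against 20, 20% against 2%, gives 80.3%.

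**3. Does a pass establish 4% or less?** Both upper limits (11.9%, 19.6%) exceed 4%. At a true rate of exactly 4%, P(X = 0) = 0.96^20 = 0.442 and P(X ≤ 1) = 0.810, so neither passing result is evidence against rates above 4%. With zero events, a one-sided 90% exact upper limit of 4% would need ln(0.10)/ln(0.96), that is 57 patients.

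**4. What a pass does support.** It rejects 20% at a one-sided exact level of 6.9%. Whether a two-sided interval at 1/20 also excludes 20% depends on level and method:

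| Interval at 1/20 | Upper limit |
|---|---|
| 90% Wilson | 19.6% |
| 90% exact | 21.6% |
| 95% Wilson | 23.6% |
| 95% exact | 24.9% |

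The 90% exact interval includes 20% because 6.9% is more than the 5% in its upper tail. Section 11.1 specifies a 95% interval without naming a method; both 95% intervals shown include 20% at 1/20.

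**5. Passing with no treatment effect, over the documents' own range.** At 18%: 0.82^19 × 4.42 = 0.102. At 19%: 0.81^19 × 4.61 = 0.084. At 20%: 0.069.

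**6. The endpoint mismatch.** One admission plus one death without admission gives X = 1 under the rule (pass) and 2/20 = 10% on the primary endpoint (90% Wilson 3.4% to 26.2%), which fails the same cut-off. The documents give no rate for death without admission. Purely as an assumption, if such deaths added 1, 2 or 5 percentage points to a 4% hospitalization rate, the chance of at most one composite event would fall from 81% to 74%, 66% or 45%.

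**The case against.** Rejecting a null in favour of a named value is common shorthand for the design alternative. The paragraph explains the 4% in its next lines, and Tables 1 and 2 print the wide intervals and the pass rates at 5%, 10% and 15%. Section 11.1 never invokes the rule: it calls for an estimate with a 95% interval, and Section 11 says that the estimates go forward to the next trial. On the endpoint, Sections 2.4 and 11.1 agree with each other, and the 2/20 case is constructed.

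Much of this stands, and it rules out several stronger readings that a reader might infer:
- That the passing data contradict 4%. They do not: 4% lies inside both 90% intervals and the estimate at 0/20 is 0%. The defect is that 4% is not established.
- That a pass never shows more than a rate below 20%. At 0/20 the 90% Wilson upper limit is 11.9%.
- That the trial will report 4% or less as its result. Section 11.1 does not say so.
- That the tables are wrong, or that deaths are not captured. The tables reproduce, and Section 6.12 and the calendar collect deaths.
- That the primary endpoint itself is undefined. It is not; the mismatch is in the rule and the wording around it.

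What does not stand is that no change is needed. The sentence states what is concluded after data are observed, and it does not label 4% as an alternative; the expectation and the power statement both use 2%. Nothing in the documents adds deaths to the rule.

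**Conclusion.** The concern holds in this form. A pass rejects 20% with a one-sided exact type I error of 6.9%. It does not establish 4% or less: the 90% Wilson upper limits are 11.9% and 19.6%, and the rule still passes 74% of the time at a true 5% and 39% at 10%. As worded, the rule can also pass an arm with 2/20 primary-endpoint events; how often cannot be computed from the documents.

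The 6.9% rests on independent binomial outcomes in 20 evaluable patients and on 20% being the right untreated rate for the composite. The documents support 18-20%, and for hospitalization only; at 18% the chance of passing with no effect is 10.2%. If deaths without admission raise the untreated composite above 20%, that chance falls below 6.9% (5.7% at 21%).

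The Section 11.1 estimate is unaffected. The change should be made, preferably before results are known, because a rule with a cut-off of one event should not be open to two readings.

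**What to change.** - Restate the rule: at most 1 of 20 patients hospitalized or dead by day 28 rejects a rate of 20% (one-sided exact type I error 6.9%). Keep this error rate distinct from the 0.25 that belongs to the between-arm Fisher test.
- Delete the conclusion of 4% or less. Describe 4% only as the true rate at which the rule has an 81% chance of passing.
- Report the observed rate with its interval, name the method, and note that at 1/20 the exclusion of 20% depends on level and method, with the four limits shown above.
- Relabel the null, the power statement and Tables 1 and 2 as hospitalization or death. Align the hospitalization-only wording in Sections 2.1, 4.1 and 6.7.
- State the assumption that the 18-20% hospitalization figure is used for the composite, and give the chance of passing with no effect: 10.2% at 18%, 8.4% at 19%, 6.9% at 20%.

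The cost is wording, table labels and one stated assumption. No new data or patients are needed. The downside is a less favourable claim after a pass.

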### 11.1. Analysis of primary endpoint:

The % of patients admitted to the hospital or died will be estimated for each arm as the proportion of patients who are hospitalized or die by day 28 since randomization along with 95% confidence interval. The secondary analysis of comparison between arms will be conducted using Fisher's exact test.

### 11.2. Analysis of the secondary and exploratory endpoints

The proportion of people with symptoms will be compared to the proportion of people without symptoms and compared using chi-squared test. Proportions with drug-related adverse events and serious adverse events will be compared using chi-squared test. All-cause mortality at day 60 will be compared using Fisher's exact test and a time to event analysis using Kaplan-Meier methods will be used to compare the two arms.

Descriptive statistics will be used to summarize and compare the exploratory endpoints.

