### 2.2. Secondary objectives

To determine if bicalutamide + camostat:

- Decrease the proportion of people with symptoms at day 7 and day 21
- Are safe to give in outpatients with COVID-19
- Decrease all-cause mortality at 60 days

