### 2.5. Secondary endpoints

- Proportion of people with symptoms at day 7 and day 21

- Proportion of drug-related AEs and SAEs
- All-cause mortality at day 60

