## 4. Treatment Plan

### 4.1. Study design

This will be a randomized, open-label study to determine if camostat+ bicalutamide decreases the proportion of people with COVID-19 who require hospitalization, compared to historical controls. Patients with symptomatic COVID-19, diagnosed as outpatients, will be randomized 1:1 stratified by gender and receipt of SOC drugs/vaccine, to treatment with standard of care alone or with camostat+bicalutamide . The schema is shown below:

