### 7.1.1. Adverse Event

An AE is defined as any undesirable sign, symptom or medical condition occurring after starting the study drug (or therapy) even if the event is not considered to be related to the study. An undesirable medical condition can be symptoms (e.g., nausea, chest pain), signs (e.g., tachycardia, enlarged liver) or the abnormal results of an investigation (e.g., laboratory findings, electrocardiogram). Medical conditions/diseases present before starting the study treatment are only considered AEs if they worsen after starting the study treatment (any procedures specified in the protocol). New medical conditions / diseases occurring before starting the study treatment but after signing the informed consent form will not be recorded as AEs.

Laboratory abnormalities: Laboratory abnormalities present at the screening visit will be recorded as pre-treatment signs and symptoms. After study treatment administration, all grade 3 and 4 clinical laboratory results that represent an increase in severity from baseline

will be reported as AEs. A grade 1 or 2 clinical laboratory abnormality should be reported as an AE only if it is considered clinically significant by the investigator (induce clinical signs or symptoms or require corrective therapy), meets the definition of an SAE, or requires the participant to have study drug discontinued or interrupted. It is expected that wherever possible, the clinical rather than laboratory term would be used by the reporting investigator (e.g., anemia versus low hemoglobin value).

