### 7.2. Relationship

The relationship of an AE to the administration of the study drug is to be assessed by the investigator according to the following definitions:

- No (unrelated, not related, no relation): The time course between the administration of study drug and the occurrence or worsening of the adverse event rules out a causal relationship and another cause (concomitant drugs, therapies, complications, etc.) is suspected.
- Yes (related): The time course between the administration of study drug and the occurrence or worsening of the adverse event is consistent with a causal relationship and no other cause (concomitant drugs, therapies, complications, etc.) can be identified.

The following factors should also be considered:

- The temporal sequence from study drug administration - The event should occur after the study drug is given. The length of time from study drug exposure to event should be evaluated in the clinical context of the event.
- Underlying, concomitant, intercurrent diseases - Each report should be evaluated in the context of the natural history and course of the disease being treated and any other disease the subject may have.
- Concomitant medication - The other medications the subject is taking or the treatment the subject receives should be examined to determine whether any of them might be recognized to cause the event in question.
- Known response pattern for this class of study drug - Clinical and/or preclinical data may indicate whether a particular response is likely to be a class effect.
- Exposure to physical and/or mental stresses - The exposure to stress might induce adverse changes in the recipient and provide a logical and better explanation for the event.
- The pharmacology and pharmacokinetics of the study drug - The known pharmacologic properties (absorption, distribution, metabolism, and excretion) of the study drug should be considered.

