## 7.5. Reporting

Information about all adverse events, whether volunteered by the subject, discovered by investigator questioning, or detected through physical examination, laboratory test or other means, will be collected, recorded, and followed as appropriate.

All adverse events experienced by subjects will be collected and reported from the first dose of study drug, throughout the study, and will only be followed for 28 days unless related to the investigational agent.

Subjects who have an ongoing adverse event related to the study procedures and/or medication(s) may continue to be periodically contacted by a member of the study staff until the event is resolved or determined to be irreversible by the investigator.

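### Section 11.2 sets people with symptoms against people without symptoms, so the only symptom analysis in the plan is not a comparison between the randomized arms

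*Combined protocol and SAP*

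**What the plan says.** The secondary objective in Section 2.2 is a treatment question: whether the combination will "Decrease the proportion of people with symptoms at day 7 and day 21". Section 2.5 lists the matching endpoint, "Proportion of people with symptoms at day 7 and day 21". Section 4.1 randomizes patients 1:1 "to treatment with standard of care alone or with camostat+bicalutamide".

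The only analysis text for this endpoint is the opening sentence of Section 11.2: "The proportion of people with symptoms will be compared to the proportion of people without symptoms and compared using chi-squared test". The plan does name the arms elsewhere: Section 11.1 describes its Fisher's exact test as a comparison between arms, and the Kaplan-Meier analysis in Section 11.2 compares the two arms.

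On safety, Section 11.2 continues: "Proportions with drug-related adverse events and serious adverse events will be compared using chi-squared test". Section 7.2 has the investigator judge each event against administration of the study drug. An event counts as related when its timing fits and "no other cause (concomitant drugs, therapies, complications, etc.) can be identified".

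**The concern.** The objective asks whether the arms differ. The analysis sentence compares the two outcome categories with each other. The neighbouring sentences on adverse events and on the day 60 mortality proportion leave the comparator unstated, so a reader can supply the arms. The symptom sentence does state a comparator, and it is not the other arm. Nothing elsewhere in the documents corrects it.

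An analyst who followed the sentence would report a p-value that does not answer the Section 2.2 question. An analyst who departed from it would be choosing the contrast, and how to treat the two visits, after an open-label trial had produced its data.

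The adverse-event sentence has a smaller problem of the same family. Patients on standard of care alone take no study drug, so no event of theirs can be related to it. A between-arm test of related events sets the treated arm against a fixed zero.

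**Working it through.** **Inputs from the documents.** Total 40 patients (Section 3), 20 per arm (Section 11), two arms (Section 4.1), chi-squared test (Section 11.2). The plan states no figure for the symptom analysis. Its only power figure, 80% for the primary endpoint, reproduces at 80.3% by exact enumeration and does not bear on this point.

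**Assumptions.** The documents give no symptom rates and no null value or significance level for this test. I take the literal test as pooled over arms, with against without symptoms (null 50%), uncorrected and two-sided at 0.05. All counts and rates below are illustrations.

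**Step 1: observed tables.** Let t and c be the numbers with symptoms in the treated and control arms, and k = t + c.

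- Literal: X² = 2(k − 20)²/20.
- Between arms: X² = 40[t(20 − c) − c(20 − t)]² / [20 · 20 · k(40 − k)].

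For t = 4, c = 16: k = 20, so the literal X² = 0. Between arms, X² = 40(4·4 − 16·16)²/(20·20·20·20) = 40·57,600/160,000 = 14.4.

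For t = c = 16: k = 32, so the literal X² = 2·144/20 = 14.4. Between arms, X² = 0.

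| Treated v control with symptoms | Literal p | Between-arm p |
|---|---|---|
| 4/20 v 16/20 | 1.00 | 0.00015 |
| 6/20 v 14/20 | 1.00 | 0.011 |
| 14/20 v 14/20 | 0.011 | 1.00 |
| 16/20 v 16/20 | 0.00015 | 1.00 |

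The first row is a 60-point risk difference (Newcombe 95% CI 30 to 77 points). The literal statistic depends on the data only through k.

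**Step 2: rejection rates.** The literal test rejects at k ≤ 13 or k ≥ 27 (p = 0.027 at 27, 0.058 at 26). Exact enumeration over two binomial arms of 20 gives:

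| True rates, control v treated | Literal rejects | Between-arm rejects |
|---|---|---|
| 70% v 70% | 70.3% | 5.3% |
| 80% v 60% | 70.7% | 29.1% |
| 90% v 50% | 72.1% | 83.8% |
| 80% v 80% | 98% | 5% |
| 80% v 40% | 19% | 75% |
| 80% v 20% | 1% | 98% |
| 50% v 50% | 4% | 4% |
| 50% v 10% | 72% | 84% |

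In the first three rows the pooled rate stays at 70%, and the literal test barely moves as the effect grows from 0 to 40 points. In the next three the control rate stays at 80%, and the literal test rejects less often as the treatment works better. In the last two the control rate stays at 50%, and it rejects more often.

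**Step 3: the within-arm reading.** If the literal test were run in each arm separately, it would reject at 5 or fewer, or 15 or more, of 20. An arm at 80% and an arm at 20% then each reject with probability 80.4%. That reading gives no contrast between arms either.

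**Step 4: drug-related adverse events (lesser point).** With x/20 related in the treated arm and 0/20 in control, X² = 40x/(40 − x). At x = 3 this is 120/37 = 3.24, below 3.84; at x = 4 it is 160/36 = 4.44 (p = 0.035). The test therefore rejects at four or more. The chance of a related event is (all-cause rate in the treated arm) × (share attributed to drug). Assume a 40% all-cause rate in both arms, so there is no excess over control:

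| Share attributed | Related rate | Related-only test rejects |
|---|---|---|
| 10% | 4% | 0.7% |
| 25% | 10% | 13% |
| 50% | 20% | 59% |
| 75% | 30% | 89% |

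An all-cause between-arm test rejects 4.8% of the time throughout. Event frequency matters too: an 80% treated-arm rate with 25% attributed gives 0.80 × 0.25 = 20% related, and so also 59%.

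**The case against.** The best defence is that this is a drafting slip. Sections 2.2, 2.5 and 4.1 supply the arms and the visits, and with and without symptoms are the natural columns of an arm-by-symptom table. No decision in the plan turns on the symptom p-value: Section 11 says the estimates will inform a larger trial, and Section 11.1 makes even the primary endpoint's between-arm test a secondary analysis. All of this stands and limits the weight of the point. It does not make the sentence right, because the sentence states a different comparison and is the only one given.

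A reader might infer that the literal test carries no information about treatment. That goes too far. With control at 80%, its rejection rate falls from 98% to 1% as the treated rate falls from 80% to 20%, so it does respond to the treated arm. What it cannot do is tell that response apart from overall symptom frequency. Nor is it systematically reversed: its direction depends on where the control rate lies.

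The rejection rates also belong to one reading of an incomplete sentence, with assumed rates. They illustrate the fault; the argument needs only that p and 1 − p are complements.

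On adverse events, a reader might infer that the related-only p-value depends on attribution alone. It does not; a drug that causes more events raises the treated count. Section 7.2 also sets a strict standard for relatedness, so the high attribution shares may be unrealistic. Finally, drug-related in Section 11.2 may qualify only the adverse events, in which case the serious-event comparison is already all-cause. What remains is that the control count of drug-related events is zero by construction.

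**Conclusion.** The point holds and should be fixed. As written, the plan's only symptom analysis is not a between-arm comparison, names no visit and confounds treatment effect with overall symptom frequency. That follows from the wording and needs no assumed rate. Its possible size, under the pooled reading with 20 per arm, is a complete mismatch: p = 1.00 for a 60-point difference between arms, and p = 0.00015 for no difference.

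The documents do not support reading this as a trial without a treatment contrast for symptoms. The intent can be inferred, and the primary endpoint, sample size and symptom data collection are unaffected.

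The adverse-event point is real but lesser. With a standard-of-care-alone control, a between-arm test of drug-related events measures treated-arm frequency combined with open-label attribution, not excess over control. The 0.7% to 89% range rests on an assumed 40% all-cause rate and assumed attribution of 10% to 75%.

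**What to change.** **Symptoms.** Replace the opening sentence of Section 11.2 with: *At day 7 and, separately, at day 21, the two randomized arms will be compared on the proportion with symptoms by chi-squared test (Fisher's exact test if expected counts are small), reporting the risk difference and its confidence interval.* The expected number with symptoms in each arm is k/2, so it falls below 5 when fewer than 10 of the 40 have symptoms; the same applies to those without symptoms when more than 30 have them. The cost is one sentence, since the study calendar in Section 10 already records symptoms at both visits. The same edit is a convenient place to say what counts as having symptoms on the Appendix A form, which has severity grades and an unknown option, and how deaths before day 21 are handled.

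**Adverse events.** Report drug-related events descriptively in the treated arm. Compare all-cause adverse events and serious adverse events between arms over one common window from randomization, using the day 3, 7, 21 and 60 contacts that Section 6.5 already schedules for all arms. This needs one sentence in Section 11.2 and a consistent start for collection. Section 7.5 says "All adverse events experienced by subjects will be collected and reported from the first dose of study drug", a date that control patients do not have, and Section 7.5.1 uses the same anchor, while Section 7.1.1 also allows the start of therapy. That mismatch is a separate and smaller drafting matter, but the common window depends on reconciling it. No new visits or patients are required.
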